Operational leaders then proposed refinements to the IVR-T approach. We designed a 3-armed randomized trial in all KPCO primary care clinics comparing a single IVR-T reminder one day prior to a primary care visit, a single reminder 3 days prior to the visit, and two reminders, delivered both 1 and 3 days prior to the visit. In addition, we assessed the effect of the intervention in all primary care sites on visit satisfaction. This trial was conducted between October and December 2016. In this study, reminders both 1 and 3 days prior to a visit reduced missed appointments by 1.4% (absolute percentage) compared to a 3-day reminder, and by 0.9% compared to a 1-day reminder alone ($p<0.001$ for both comparisons). The effectiveness of 2 reminders was particularly strong in individuals who were at predicted high risk of missing appointments. For these individuals, 2 reminders reduced missed appointments by 4.5% and 3.7%, respectively. Based on these findings, 3-day and 1-day IVR-T reminders are now standard for all primary care visits in KPCO.

Clinical and operational leaders have now requested the IHR develop IVR-T interventions to reduce missed GI endoscopy procedures in KPCO. GI endoscopies (both upper and lower endoscopy) are performed at Franklin, Rock Creek, and Lone Tree facilities. GI clinic managers have tracked “appointment loss,” defined as prior-day cancellations, same-day cancellations, or missed visits since 2013. The trends over this period are shown in Table 1:

Table 1: Appointment Loss in GI Procedure Clinics, KPCO, 2013-2018

Site	2013	2014	2015	2016 (January-May)	2017	2018 (January- mid-October)
Franklin	8.7%	9.6%	8.8%	9.6%	x	Total = 9.2% No show – 2.5% Same-day cancel – 2.6% Prior day cancel – 4.1% N = 7612
Rock Creek	6.4%	6.4%	5.3%	5.9%	x	Total = 4.8% No show – 1.2% Same-day cancel – 1.2% Prior day cancel – 2.4% N = 7592
Lone Tree	6.0%	7.4%	5.2%	6.5%	x	Total = 6.5% No show – 1.2% Same-day cancel – 1.0% Prior day cancel – 3.2% N = 9283

These rates have been relatively constant over time. They represent substantial inefficiency for the KPCO system and prevent many members from receiving their procedure in a timely way. Each unfilled slot represents an estimated cost of about \$1200 to KPCO.

This problem has persisted despite the use of IVR-T reminders and live calls from GI clinic nurses. In October 2018, the IVR-T protocol for GI procedures includes a single IVR-T reminder, 7 days prior to the appointment. If a text message cannot be sent due to a text-incapable phone number or a text failure, members receive an IVR telephone call. Both text and call provide the date, time and location of the appointment. The text includes a number to call to reschedule or cancel. The call allows the member to transfer into the GI scheduling line. If the appointment is for a colonoscopy, both the text and the IVR call contain additional information about the bowel preparation and the need to bring a driver to take the member home after the procedure. This automated reminder is supplemented by live phone calls 5 business days in advance from GI clinic nurses when their workflow allows it. These calls are most common at the Rock Creek clinic. The nurses do not use pre-defined criteria to decide who to call, they simply try to call any patients they can reach. The proportion of members currently receiving these calls is unknown.

This protocol and IRB modification describes a series of projects to optimize the use of reminders to improve efficiency in GI endoscopy. Collectively, their goal is to improve operational efficiency by reducing missed appointments and late cancellations.

LITERATURE REVIEW

The published literature addresses three general questions about missed appointments in GI endoscopy clinics:

- a. What is the incidence of missed appointments and/or late cancellations?
- b. What are the predictors of missed appointments and/or late cancellations?
- c. Are interventions effective in reducing missed appointments or late cancellations?

These studies take place in three clinical contexts and settings: 1) Studies of appointment-keeping in endoscopy clinics; 2) Studies of appointment-keeping in GI consultation practices; and 3) Studies of colonoscopy completion after positive FOBT or FIT testing. The first studies are most relevant. The second group may identify risk factors and intervention strategies that also apply to endoscopy appointments. In the third group, endoscopy appointment-keeping is one step in a care continuum that begins with *referral* after a positive test for occult blood, then *scheduling* of an appointment for flexible sigmoidoscopy or colonoscopy, then evaluation of the *adequacy of the prep*, and finally completion of the procedure.

Key findings and references:

- a. Most studies have been conducted in academic settings, the VA, or safety-net delivery systems. None have been conducted in integrated, private systems such as KPCO.
- b. The incidence of non-attendance at endoscopic procedures varies widely, depending in part on whether late cancellations within a few days of the procedure are included in the definition. The incidence of no-shows on the day of the procedure ranges from 4% to 23%, with most studies reporting rates of 8-10%. (Lee, Gurudu, Griffin, Blumenthal, Childers, Partin) In a large VA study, the incidence of cancellations was 32%. (Partin) Several studies did not distinguish between no-shows and cancellations (Griffin, Childers) and reported aggregated rates of 16%-42% for all causes of non-attendance.
- c. Most studies identified clinical and procedural predictors of non-attendance. Most conducted multivariable analyses, but only one study (Blumenthal) developed and validated a clinical prediction rule for missed endoscopy appointments. Patient-level predictors of missed or cancelled appointments in multiple studies included: minority race or ethnicity, unmarried/unpartnered, Medicaid or no health insurance, and presence of a mental health or substance abuse disorder. The clinical indication for the procedure was a predictor in some but not all studies. Clinic and system-level predictors included: longer wait time between scheduling and procedure; prior missed endoscopy appointments, and prior missed appointments in other settings. A large VA study also found substantial variation between VA facilities. (Partin) The one reported prediction rule incorporated patient-level and system-level variables and had a c-statistic of 0.75 in the development set, and 0.70 in the validation set, indicating moderate accuracy in discriminating individuals at high risk of missing endoscopy appointments from those at lower risk. (Blumenthal)
- d. Some form of reminder (letter or phone call) was commonly provided as a baseline in these studies. One randomized trial compared a “live” nurse reminder call to IVR

outreach 3 days or 7 days prior to the endoscopy appointment – no differences were found between groups. (Griffin) A before-after study found that no-shows decreased from 16.5% to 12.8% after instituting a nurse call. This study also quoted the lost revenue from a missed appointment as approximately \$1000 for colonoscopy and \$780 for upper endoscopy. An RCT of a telephone call 1 day prior to colonoscopy to educate about bowel prep showed that adequate prep was greater in the intervention than control group (81.6% vs. 70.3%), as was polyp detection (38.0% vs. 24.7%).

e. In summary

- The prevalence of missed endoscopy appointments or late cancellations is already lower in KPCO than in most published studies.
- The most important clinical predictors used in other studies are available through KPCO electronic data sources.
- The only reported prediction rule to identify high-risk patients for missing endoscopy appointments had only moderate accuracy.
- A relevant randomized trial showed no difference between a single “live” reminder and a single IVR call 3 days or 7 days prior to the visit.
- Another randomized trial suggests that a live call the day prior to the procedure can increase the adequacy of the bowel prep.

PROJECT QUESTIONS AND HYPOTHESES

This project will address the following question:

Does an “enhanced” IVR-T protocol differ in effectiveness from the standard IVR-T protocol in reducing missed appointments and late cancellations for GI endoscopy?

Hypothesis 1: The enhanced IVR-T protocol will be more effective.

RESEARCH DESIGN AND METHODS

We will conduct a randomized trial over a 6-month period (March through September 2019) in the 3 GI endoscopy clinics (Franklin, Rock Creek, and Lone Tree). All members currently receive a text reminder 7 days prior to their procedure, which rolls over to a telephone reminder if the text cannot be delivered or the member’s phone is not text-enabled. Members will be randomized either to receive this standard IVR-T protocol or to receive an enhanced reminder protocol.

Inclusion criteria:

- a. Members scheduled for any GI procedure (upper endoscopy, colonoscopy, or both), with or without anesthesia, at all three clinical sites (Franklin, Rock Creek, Lone Tree) will be included if their procedure is scheduled \geq 2 days prior to the procedure. The IVR-T protocol will be adapted based on the wait time between appointment scheduling and the date of the procedure.
- b. Members with all clinical indications (screening, diagnosis, or surveillance), will be included.

Exclusion criteria:

- a. KPCO members who request not to participate in research or not to receive IVR-T or email outreach
- b. KPCO members in the “break the glass” or “code pink” protocols.
- c. Members whose procedure is scheduled $<$ 2 days prior to the procedure.

Randomization: Beginning in March 2019 (or on completion of all necessary design steps), we will use the randomization algorithm in the Structured Query Language program that manages the IVR relational database to assign each visit for a procedure at all three sites to one of the two interventions. Since members with multiple procedures on different days during the study period could receive different interventions for different visits, we will limit the statistical analysis to the first randomized appointment during the project period. Randomization will be stratified by clinic site.

Intervention content

- a. **Standard reminder protocol (usual care):** Members randomized to this arm of the study will receive a single text message that “rolls over” to an IVR automated phone call if the text cannot be delivered. This message will be delivered 7 business days prior to

the appointment. This replicates the current protocol for GI procedures. Of note, members who schedule appointments within 7 days of the procedure currently receive no reminders.

- b. **Enhanced reminder protocol:** The enhanced reminder protocol will include multiple reminders, multiple reminder modalities, and motivational messages. The timing of reminders will depend on the wait time between the date the appointment is made and the date of the appointment, as shown in Table 2.

Table 2. Timing of reminders for intervention group

Wait time between date appointment made and date of visit	Email †	IVR-1	IVR-2	IVR – Prep (colon only)
≥ 15 calendar days	14 calendar days	7 business days	5 business days	1 calendar day
8-14 calendar days	6-12 calendar days	5 business days	3 business days	1 calendar day
7 calendar days	5 calendar days	5 business days	3 business days	1 calendar day
6 calendar days	4 calendar days	2-3 business days (2 days if appt on Monday)	1 business day	1 calendar day
5 calendar days	3 calendar days	1 business day	x	1 calendar day
4 calendar days	2 calendar days	1 business day	x	1 calendar day
3 calendar days	1 calendar day	0-1 business day (No IVR if appt on Monday)	x	1 calendar day
2	x	x	x	1 calendar day
0-1 days	x	x	x	X

- An email reminder will be sent to all members who have provided their personal email information according to the schedule in Table 2.
- For IVR-T reminders, the rationale for choosing business days (Monday through Friday) rather than calendar days is that the GI appointment desk is only open on business days to cancel or reschedule procedures.
- Members scheduled for colonoscopy will also receive a single IVR-T reminder to begin their bowel prep the morning of the calendar day prior to the procedure.
- Brief motivational messages will be added to email, text and telephone messages. These messages will be “generic” rather than tailored for the clinical indication or type of procedure.
- For the duration of this intervention, the GI clinic will discontinue all live pre-procedure reminders so that we can assess the effectiveness of a purely automated intervention. Staff will continue post-procedure calls to assess service quality. Selective live reminders for members at high risk of missed appointments will be assessed in Step 3 of this project.

Intervention delivery: All interventions by email, text and telephone will be delivered by secure messages from the Automated Communication Technology (ACT) team in the KPCO

Institute for Health Research. At present, GI clinic nurses or staff make live reminder calls to some members as time allows; these calls will be stopped for the duration of the Step 1 trial.

Over the 6-month period of the project, we estimate that approximately 2300 visits per month will be scheduled across the 3 participating sites. After anticipated exclusions (10% of total cases), we estimate that there will be approximately 2100 eligible appointments per month. We project that the study will run from March 8, 2019 through September 7, 2019 to achieve the proposed sample size of approximately 13,000 appointments. The duration of the study will be dictated by the number of appointments necessary to detect an operationally significant reduction in the rate of appointment loss, as described in the sample size calculations below. We will monitor recruitment during the study and adjust the duration of the randomization period as necessary to achieve the projected sample size.

9. Study Measures

Outcome variable: The primary outcome for the study will be “appointment loss”, defined by GI leaders as the combined rate of prior day cancellations, same-day cancellations, and missed clinic appointments (“no shows”). The rationale for this outcome definition is that it is difficult to schedule new procedures within this time frame. As a secondary outcome, we will assess the adequacy of the bowel preparation for colonoscopy only.

Covariates: To describe the project participants and identify clinically and operationally relevant subgroups, we will measure patient covariates that we have used in prior IVR-T evaluations in primary care clinics, as well as variables specific to the GI clinic setting. These variables are listed in Appendix 1. All variables will be drawn from the IHR Virtual Data Warehouse (VDW), KPCO appointment scheduling system, or endoscopy data from Clarity.

10. Sample size and statistical analysis

Sample size calculation: As shown in Table 1, “appointment loss” in the 3 GI clinics has been 6.8% from January – mid-October 2018. Across sites, approximately 2580 procedures/month were scheduled, and 175 were missed. Using standard parameters for Type 1 error (0.05, two-sided) and Type 2 error (0.20), the necessary sample to detect differences between standard and enhanced IVR-T protocols is:

Table 3. Sample Size Estimates

Detectable difference in appointment loss	N total (per group)	Duration of project (months)
3% absolute difference (6.8% vs. 3.8%)	2654 (1327)	1.3
2% absolute difference (6.8% vs. 4.8%)	5644 (2822)	2.7
1% absolute difference (6.8% vs. 5.8%)	21244 (10622)	10.1
20% relative difference*	11112 (5556)	5.3

(6.8% vs. 5.4%)		
-----------------	--	--

*Effect consistent with prior KPCO trials and systematic reviews of missed appointment interventions

Based on these calculations, a 6-month study will provide statistical power to detect a 20% relative difference in appointment loss.

Analytic plan Statistical analyses will be consistent with approaches used in prior IVR-T interventions. Patient demographic and clinical characteristics will be compared between the 2 groups using *t*-tests for normally distributed continuous variables, Wilcoxon rank tests for non-normally distributed continuous variables, and chi-square tests for discrete variables. We will assess the effectiveness of the intervention across the 3 participating clinics, after adjusting for predictors of missed appointments/late cancellations. To estimate the number of additional kept visits and available appointments per week that would result if the most effective intervention were implemented for all visits that met inclusion criteria, we will multiply the average number of visits at each clinic by the sum of the rate reduction in missed appointments and the rate increase in cancelled appointments at that clinic.

We will conduct three planned subgroup analyses:

1. We will develop a multivariable logistic regression model to predict appointment loss using approaches similar to prior IVR-T interventions. Clinic site will be included as a fixed effect. We will include linear and quadratic terms for continuous predictors and include both terms in the final model if statistically significant. Missing values for each predictor will be included as a separate category. Backward selection with Wald chi-square tests will guide the selection of predictors. The final prediction model will include an indicator variable for treatment group and all covariates with *p*-values <0.05. The discrimination of the model will be assessed with the *c*-statistic. We will use this prediction rule to stratify participants into risk quartiles and will assess the effectiveness of the intervention in each quartile.
2. We will assess the effectiveness of the intervention in each of the 3 participating clinics, after adjusting for predictors of missed appointments/late cancellations, to provide preliminary information on site-level factors that may modify intervention effectiveness.
3. We will analyze the effectiveness of the intervention in the subgroup of individuals who schedule their endoscopies \leq 7 days prior to the procedure, since these individuals will receive no reminders under the standard protocol.

Human subjects

The standard reminder protocol includes a text message that “rolls over” to an IVR automated phone if the text cannot be delivered. The GI Clinic has received permission from the KPCO Compliance Office to send emails to the private email addresses of KPCO members.

Study Risks: This study utilizes current standard protocols for contacting KPCO members and data collected during the course of routine clinical care to improve efficiencies in the delivery and quality of care for patients. Therefore, the primary risk of this study is the potential for loss of confidentiality and privacy of a member, through a loss or inappropriate disclosure of study data. There are no known risks to investigators or staff.

Protection against Risks: The primary protection against a breach of privacy and confidentiality is in the structure of the data itself. The data extracted will include the minimum necessary to conduct the described research. Additional procedures will be in place to further protect members from a breach of confidentiality: 1) all data in study datasets will be identified only by a study-assigned unique ID number and will not include the name or medical record number of the subject; 2) a crosswalk table linking the study ID to a patient medical record number will be separately maintained on password-protected computers only accessible to project staff; 3) all members of the project team have completed mandated training procedures and certifications, including special compliance training; new research team members (if any) will complete currently mandated training procedures and certifications prior to working on the study; and 4) the written study protocol will be reviewed, approved, and monitored by the IRB. Furthermore, only aggregate data will be released in any public forum or publication.

Study Benefits: Members may receive improved quality of their overall care with Kaiser through this study. The results could promote increased health and wellness.

Risk-Benefit Justification: This investigation involves minimal risks to any member. The benefits outweigh the minimal risks to members.

Informed Consent: This study will request a waiver of individual informed consent as in prior projects because it is low risk, has a large number of members and is a comparison of standard practices. This is a study of improving efficiencies and therefore the risks to subjects are minimal. It is estimated that up to 15,000 members will be eligible for the study, which is not feasible to contact to obtain written informed consent. This study is intended to enhance the quality of care for patients and standard practices.

HIPAA Authorization: This study will request a waiver of patient authorization to obtain private information, also known as a waiver of HIPAA authorization. This waiver is requested because the study involves no more than a minimal risk to the privacy of individuals.

Dissemination and implementation

Operational leaders ([name], [name]) have actively participated in intervention design and can lead implementation efforts to sustain the intervention in KPCO if it is effective, as has been the case for prior missed appointment interventions in KPCO. The findings of this evaluation will be shared with KPCO organizational sponsors. We will also prepare a paper for publication based on these findings.

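### Table 1: Lone Tree's 2018 loss components add to 5.4%, not the stated 6.5%, so the 6.8% baseline needs a source check, although the effect on power is small

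*Combined protocol and SAP*

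**What the plan says.** Table 1, in the background text, breaks down 2018 appointment loss (January to mid-October) by clinic:

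- Franklin: "Total = 9.2% No show – 2.5% Same-day cancel – 2.6% Prior day cancel – 4.1% N = 7612"
- Rock Creek: "Total = 4.8% No show – 1.2% Same-day cancel – 1.2% Prior day cancel – 2.4% N = 7592"
- Lone Tree: "Total = 6.5% No show – 1.2% Same-day cancel – 1.0% Prior day cancel – 3.2"%, with N = 9283

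The text introducing the table describes appointment loss as "defined as prior-day cancellations, same-day cancellations, or missed visits since 2013". Section 9 (Study Measures) defines the primary outcome in the same way, as "the combined rate of prior day cancellations, same-day cancellations, and missed clinic appointments". Neither definition has a further category.

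Section 10 (Sample size calculation) cites Table 1 and says that loss in the three clinics "has been 6.8% from January – mid-October 2018", and that "approximately 2580 procedures/month were scheduled, and 175 were missed". All four rows of Table 3 use 6.8% as the control rate. The design row is the 20% relative difference, at 5,556 per group. The methods text plans about 13,000 appointments over six months.

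**The concern.** Under the plan's own definition, a clinic's total should be the sum of its three components. That holds at Franklin and Rock Creek but fails at Lone Tree, the largest of the three clinics. The Lone Tree total feeds the pooled baseline, and the baseline is the control rate behind the whole sample size table. For a fixed relative effect, a lower control rate means a smaller absolute difference and therefore a larger required sample. If the Lone Tree total is the wrong figure, the requirement for the 20% relative target is understated for any given method of calculation.

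**Working it through.** **1. Do the components add up?** (Inputs: Table 1, 2018 column.)

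- Franklin: 2.5 + 2.6 + 4.1 = 9.2, stated 9.2.
- Rock Creek: 1.2 + 1.2 + 2.4 = 4.8, stated 4.8.
- Lone Tree: 1.2 + 1.0 + 3.2 = 5.4, stated 6.5.

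The gap is 1.1 points, or 0.011 × 9,283 ≈ 102 appointments. With one-decimal rounding the components can reach at most 1.25 + 1.05 + 3.25 = 5.55%, while a total printed as 6.5% is at least 6.45%. Rounding therefore leaves a gap of about 0.9 points or more.

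**2. Reproduce the plan's baseline.** The pooled rate is the mean of the site rates weighted by N, where N = 7,612 + 7,592 + 9,283 = 24,487.

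- With Lone Tree at 6.5%: (7,612 × 9.2 + 7,592 × 4.8 + 9,283 × 6.5) / 24,487 = 6.81%. This reproduces 6.8%.
- Assuming that January to mid-October is 9.5 months: 24,487 / 9.5 ≈ 2,578 procedures and about 175.6 losses per month, matching the stated 2,580 and 175.
- With Lone Tree at 5.4%: 6.395%, that is 6.4%, or about 165 losses per month.

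**3. Sample size for a 20% relative reduction.** Two proportions, pooled variance, two-sided alpha 0.05, 80% power, 1:1 allocation (assumed from Table 3's equal groups):

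n per group = [1.96 √(2p̄(1−p̄)) + 0.8416 √(p₁(1−p₁) + p₂(1−p₂))]² / (p₁−p₂)²

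- 6.8% to 5.44%: 4,876 per group.
- 6.4% to 5.12%, with p̄ = 5.76%: [1.96 × 0.32949 + 0.8416 × 0.32937]² / 0.0128² ≈ 5,200 per group, 10,400 in total.

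At the plan's 2,100 eligible appointments per month, 10,400 takes just under 5 months.

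**4. Power for that 20% relative reduction.**

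| Per group | From 6.8% | From 6.4% |
|---|---|---|
| 5,556 (Table 3 design row) | 84.9% | 82.5% |
| 6,300 (2,100 × 6 / 2) | 89.0% | 86.9% |
| 6,500 (13,000 / 2) | 89.9% | 87.9% |

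**5. Absolute-difference rows.** By the same formula, moving the baseline from 6.8% to 6.4% changes n per group from 875 to 812 (3 points), 2,143 to 2,004 (2 points) and 9,266 to 8,715 (1 point). All three fall.

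**6. A caution about the printed Ns.** Table 3's figures do not reproduce for the decreases in its labels; 6.8% vs 5.4% needs 4,587 per group, not 5,556. They reproduce exactly for increases of the same size from 6.8%: 1,327, 2,822, 10,622 and 5,556 for 9.8%, 8.8%, 7.8% and 8.2%. That is a separate matter, but it affects the comparison here. By that mirrored calculation a 20% relative change from 6.4% needs 6,270 per group (12,540 in total), which exceeds 5,556 but is still below 6,500. The absolute rows still fall, to 1,268, 2,689 and 10,083.

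**The case against.** The best defence is that the total may well be right. The 6.8% rate and the 175 losses per month both agree with 6.5%. The documents do not say how 175 was obtained; if it was a direct count, it supports the total. A single-digit slip would be enough: a prior-day figure of 4.2% instead of 3.2% gives 6.4%, which matches 6.5% within rounding. If so, only a background cell is wrong and Table 3's baseline is untouched. This argument stands, and it is why the point cannot go beyond a conditional one. It does not show that the total is right, because 175 could equally have been derived from the 6.5%. Lone Tree's earlier rates (6.0%, 7.4%, 5.2%, 6.5%) include both candidates in their range.

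A second defence is that the baseline is soft in any case. The 2018 rates arose while nurses made live calls to an unknown share of members, and those calls stop during the trial. A difference of 0.4 points is modest beside that. This also stands as a comment on size, but it does not excuse a table that contradicts itself.

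Two stronger readings are tempting. A reader might infer that the trial is underpowered; the calculations in steps 3 and 4 do not support that. A reader might also infer that the lower baseline compounds with limiting the analysis to each member's first randomized appointment. The documents give no rate of repeat appointments, so no shortfall can be shown on that ground.

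**Conclusion.** The inconsistency is real: at least one of the four Lone Tree percentages for 2018 is wrong, and the documents do not show which. The 6.8% baseline holds if a component is wrong and becomes 6.4% if the total is wrong.

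Either way the consequence is minor. In the less favourable case the 20% relative target costs about two points of power, remains well above 80% at the planned size, and leaves the six-month power claim intact. The effect on Table 3 is not uniformly adverse, since only the relative-difference row moves the wrong way. These conclusions assume 1:1 allocation, 9.5 months for the monthly figures, and about 13,000 appointments actually analysed.

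**What to change.** Check the Lone Tree 2018 source counts before relying on the baseline.

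- If the total is wrong: correct it to 5.4%, restate the pooled baseline as 6.4% and the monthly losses as about 165, and recompute all four rows of Table 3 and the power statement.
- If a component is wrong: correct that component in Table 1 and keep 6.8%.

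The cost is one data query and, at most, a restated table with a slightly lower power figure. On these calculations neither outcome requires a longer study or a larger target sample.

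### Some short-notice upper-endoscopy visits are eligible and randomized but are sent no reminder in either arm, which dilutes the contrast slightly overall and more in the subgroup booked 7 or fewer days ahead

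*Combined protocol and SAP*

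**What the plan says.** **Eligibility and randomization (Research Design and Methods).** Inclusion criterion a covers "Members scheduled for any GI procedure (upper endoscopy, colonoscopy, or both), with or without anesthesia", provided the booking is made at least 2 days ahead. Shorter bookings are excluded. The algorithm will "assign each visit for a procedure at all three sites to one of the two interventions", stratified by clinic site only.

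**Enhanced arm (Table 2 and its bullets).** In the 2-day row, email, IVR-1 and IVR-2 are all crossed out. The one remaining entry is in the column "IVR – Prep (colon only". A bullet below the table confirms who gets it: "Members scheduled for colonoscopy will also receive a single IVR-T reminder to begin their bowel prep". In the 3-day row, the IVR-1 entry reads "0-1 business day (No IVR if appt on Monday", IVR-2 is crossed out, and email goes only to members who have supplied an address. The 0-1 day row is entirely crossed out.

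**Standard arm (Intervention content, a).** The protocol notes that "members who schedule appointments within 7 days of the procedure currently receive no reminders". The section also stops all live pre-procedure reminders for the duration of the trial.

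**Analysis (section 10).** Planned subgroup 3 takes everyone who books 7 or fewer days ahead, whatever the procedure, "since these individuals will receive no reminders under the standard protocol". Nothing in section 10 identifies, counts or removes visits for which the enhanced schedule is also empty.

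**The concern.** A visit for which both arms send nothing cannot contribute to the effect of the reminders. It adds appointments and loss events to both arms and pulls the estimated difference towards zero.

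The primary analysis is exposed to this, but subgroup 3 more so. Its stated rationale is that late bookers get nothing under the standard protocol, so the natural reading is reminders against none. For the visits at issue it is none against none. If the subgroup result is weak, a reader could conclude that reminders do not help late bookers when some of those in the enhanced arm were never due to receive one.

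The mismatch looks like an oversight. The 0-1 day row of Table 2 is empty, and those bookings are excluded. The 2-day cutoff works for colonoscopy, where a prep message is still sent, but not for upper endoscopy alone. The documents give no rationale for the cutoff, so this is an inference.

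**Working it through.** **1. Which visits have no contrast**

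| Visit | Enhanced arm | Standard arm |
|---|---|---|
| Upper endoscopy only, booked 2 days ahead | nothing (prep message is colonoscopy only) | nothing |
| Upper endoscopy only, booked 3 days ahead for a Monday, no email on file | nothing (no IVR, no email, no prep message) | nothing |
| Colonoscopy, or both procedures, booked 2 days ahead | prep message | nothing |

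The first two rows are eligible and randomized. The third keeps a contrast and is not at issue.

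**2. The plan's own sample-size figure**

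Section 10 gives two-sided type 1 error 0.05, type 2 error 0.20, and 5,556 per group for 6.8% vs 5.4%. The two-proportion formula with pooled variance gives 4,587 per group for those rates, and 4,876 if the 20% reduction is taken exactly (5.44%). The stated 5,556 is what the formula gives for 6.8% vs 8.2%, an increase of the same size. The stated number is therefore larger than the labelled difference needs. That is a separate matter, but it means there is some slack here. Below I use 6.8% vs 5.44% and about 6,500 per arm (13,000 appointments, equal groups).

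**3. Dilution in the primary analysis**

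Let f be the share of analysed visits with no contrast. The documents do not give it; the values below are assumptions. With the same baseline risk in these visits, the enhanced-arm rate is

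p_E = f × 6.8% + (1 − f) × 5.44%,

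so the observed reduction is (1 − f) times the true one. Power = Φ{(d√n − 1.96√[2p̄(1 − p̄)]) / √[p_S(1 − p_S) + p_E(1 − p_E)]}, where p_S = 6.8%, d = p_S − p_E and p̄ is the mean of the two rates. At f = 2%: p_E = 0.02 × 6.8% + 0.98 × 5.44% = 5.467%.

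| f | Observed relative reduction | Needed per arm (80% power) | Power, visits kept (6,500) | Power, visits excluded (6,500 × (1 − f)) |
|---|---|---|---|---|
| 0 | 20.0% | 4,876 | 89.9% | 89.9% |
| 2% | 19.6% | 5,087 | 88.6% | 89.3% (6,370) |
| 5% | 19.0% | 5,430 | 86.5% | 88.4% (6,175) |
| 10% | 18.0% | 6,082 | 82.5% | 86.6% (5,850) |

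With the visits kept, power falls below 80% only at f of about 12.9%.

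**4. Sensitivity to the equal-risk assumption**

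The literature review lists longer wait as a predictor of non-attendance, so short-wait visits may carry lower risk. If their risk were half (an assumption), the observed reduction is 0.20(1 − f) / [(1 − f) + 0.5f]. At f = 10% that is 0.18 / 0.95 = 18.9% instead of 18.0%. Higher risk would move it the other way.

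**5. Subgroup 3**

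All the no-contact visits were booked 2 or 3 days ahead, so all lie in this subgroup. If the subgroup is a share S of visits, its no-contact share is g = f / S, which exceeds f whenever S is below 1. For illustration, assume S = 10% (650 per arm) and a true 20% reduction:

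| g | Corresponding f | Observed reduction | Power, visits kept | Power, visits excluded |
|---|---|---|---|---|
| 0 | 0 | 20% | 17.4% | 17.4% |
| 10% | 1% | 18% | 14.8% | 16.1% (585) |
| 20% | 2% | 16% | 12.5% | 14.8% (520) |
| 30% | 3% | 14% | 10.5% | 13.5% (455) |

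Under these assumptions exclusion does not rescue power. What it restores is the estimand: the effect of sending late bookers a reminder.

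**The case against.** The strongest defence is that the trial compares two reminder policies. The enhanced policy is expressly adapted to wait time, and section 10 projects the gain if it were applied to all visits meeting the inclusion criteria. On that view, visits for which the schedule sends nothing belong in the comparison. This stands. The all-randomized comparison is a valid estimate of the policy effect, and a reader who infers that the primary result would be biased, or the trial seriously underpowered, goes further than the documents allow. They give no distribution of lead time, procedure type or email availability. Nothing in them supports a share of 10% or more in the primary analysis, and at 2% the loss is about 1.3 points of power (89.9% to 88.6%).

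It also stands that excluding visits after randomization and making that the primary analysis would be a debatable trade, even with a baseline rule. For that reason I do not recommend it.

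The policy argument does not cover subgroup 3. That analysis is justified by the absence of reminders in the standard arm, and for these visits the enhanced arm has none either. Low power is probably the subgroup's main limit, but that makes a weak result easier to misread.

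Another possible answer is the Appendix 1 note on appointment lead time, which says to exclude values under 10 days. If applied, it would remove these visits. It would also contradict the 2-day inclusion criterion and leave subgroup 3 empty, so it adds an inconsistency and does not solve the problem.

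**Conclusion.** The point holds as one of dilution and interpretation. Two identifiable groups of eligible visits are randomized between no reminder and no reminder; this follows directly from the inclusion criteria, Table 2, the standard protocol and the suspension of live calls. The randomized comparison remains unbiased.

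The cost to the primary analysis is probably slight: under equal baseline risk, a true 20% reduction is seen as 19.6% at f = 2% and 18.0% at f = 10%. These shares are assumptions, and lower risk in short-wait visits would soften the dilution. The proportionate effect on subgroup 3 is larger because every such visit falls in it, but its size cannot be fixed without the booking data.

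**What to change.** **Before randomization.** Align eligibility with Table 2. In both arms, exclude upper-endoscopy-only visits booked 2 days ahead, and those booked 3 days ahead for a Monday with no email on file. Use only baseline facts: procedure type, wait, weekday of the appointment and email on file. This treats them as 0-1 day bookings are already treated. Add procedure type and email on file to Appendix 1, which lists neither; delivering Table 2 already requires both. In the section 10 projection of visits gained, multiply the rate change by the number of visits in the same restricted set, since applying it to all visits would overstate the gain.

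**If visits have already been randomized.**
- Keep the all-randomized analysis as primary and describe it as the effect of the policy.
- Apply the baseline restriction to subgroup 3, and to the primary comparison as a sensitivity analysis.
- Do not replace a removed first appointment with the member's later one.
- Report the number of no-contact visits by arm, overall and in subgroup 3.
- Match the multiplier in the projection to the visit set that produced the rate.

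**In either case.** Reconcile the Appendix 1 lead-time note with the 2-day criterion and subgroup 3.

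**Cost.** One filter in the randomization query and a sentence in the criteria, or one analysis-set rule and a count. A small number of appointments is lost and the eligible population is slightly narrower. The plan already allows the randomization period to be extended to reach the target.
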